9.2.1.3.2 Reactogenicity (Solicited Reactions From Day 0 to Day 7 After Each Vaccination)

After the first vaccination, subjects will be provided with a digital thermometer and a flexible ruler, and after each vaccination, subjects will be provided with a DC. Subjects will be instructed how to use them. The following items will be recorded by the subjects in the DC on the day of vaccination and for the next 7 days, as applicable (ie, solicited injection site reactions from Day 0 through Day 7; solicited systemic reactions between the first and the second injections, between the second and the third injections, and up to 7 days after the remaining injections), until resolution:

- Daily temperature, with the route by which it was taken, preferably oral route
- Daily measurement or intensity grade of all other solicited injection site and systemic reactions
- Action taken for each event (eg, medication)

For solicited reactions still ongoing after the solicited period, daily intensity will be recorded in the DC until resolution of the reaction.

The action(s) taken by the subject to treat and/or manage any **solicited reactions** will be classified in the CRB using the following list (all applicable items should be checked):

- None
- Medication
- Health care provider contact
- Hospitalized
- Discontinuation of study vaccination

[Table 9.1](#) and [Table 9.2](#) present, respectively, the injection site reactions and systemic reactions that are prelisted in the DCs and CRB, together with the intensity scales.

Table 9.1: Solicited injection site reactions: terminology, definitions, and intensity scales

CRB term (MedDRA lowest level term [LLT])	Injection site pain	Injection site erythema	Injection site swelling
Diary card term	Pain	Redness	Swelling
Definition	Pain either present spontaneously or when the injection site is touched or injected limb is mobilized	Presence of a redness including the approximate point of needle entry	Swelling at or near the injection site Swelling or edema is caused by a fluid infiltration in tissue or cavity and, depending on the space available for the fluid to disperse, swelling may be either soft (typically) or firm (less typical) to touch and thus can be best described by looking at the size of the swelling
Intensity scale*	Grade 1: A type of adverse event that is usually transient and may require only minimal treatment or therapeutic intervention. The event does not generally interfere with usual activities of daily living. Grade 2: A type of adverse event that is usually alleviated with additional therapeutic intervention. The event interferes with usual activities of daily living, causing discomfort but poses no significant or permanent risk of harm to the research participant. Grade 3: A type of adverse event that interrupts usual activities of daily living, or significantly affects clinical status, or may require intensive therapeutic intervention.	Grade 1: ≥ 25 to ≤ 50 mm Grade 2: ≥ 51 to ≤ 100 mm Grade 3: > 100 mm	Grade 1: ≥ 25 to ≤ 50 mm Grade 2: ≥ 51 to ≤ 100 mm Grade 3: > 100 mm

* For the subjective reaction of pain, subjects will record the intensity level (Grade 1, 2, or 3) in the diary card. For the measurable reactions of redness and swelling, they will record just the size of the reaction, and the classification as Grade 1, 2, or 3 will be assigned at the time of the statistical analysis

Table 9.2: Solicited systemic reactions: terminology, definitions, and intensity scales

CRB term (MedDRA lowest level term [LLT])	Fever	Headache	Malaise	Myalgia
Diary card term	Temperature	Headache	Feeling unwell	Muscle aches and pains
Definition	Elevation of temperature to $\geq 38.0^{\circ}\text{C}$ ($\geq 100.4^{\circ}\text{F}$)	Pain or discomfort in the head or scalp. Does not include migraine.	General ill feeling. Malaise is a generalized feeling of discomfort, illness, or lack of well-being that can be associated with a disease state. It can be accompanied by a sensation of exhaustion or inadequate energy to accomplish usual activities.	Muscle aches and pains are common and can involve more than one muscle at the same time. Muscle pain can also involve the soft tissues that surround muscles. These structures, which are often referred to as connective tissues, include ligaments, tendons, and fascia (thick bands of tendons). Does not apply to muscle pain at the injection site which should be reported as injection site pain.
Intensity scale*	Grade 1: $\geq 38.0^{\circ}\text{C}$ to $\leq 38.4^{\circ}\text{C}$, or $\geq 100.4^{\circ}\text{F}$ to $\leq 101.1^{\circ}\text{F}$ Grade 2: $\geq 38.5^{\circ}\text{C}$ to $\leq 38.9^{\circ}\text{C}$, or $\geq 101.2^{\circ}\text{F}$ to $\leq 102.0^{\circ}\text{F}$ Grade 3: $\geq 39.0^{\circ}\text{C}$ or $\geq 102.1^{\circ}\text{F}$	Grade 1: A type of adverse event that is usually transient and may require only minimal treatment or therapeutic intervention. The event does not generally interfere with usual activities of daily living. Grade 2: A type of adverse event that is usually alleviated with additional therapeutic intervention. The event interferes with usual activities of daily living, causing discomfort but poses no significant or permanent risk of harm to the research participant. Grade 3: A type of adverse event that interrupts usual activities of daily living, or significantly affects clinical status, or may require intensive therapeutic intervention.	Grade 1: A type of adverse event that is usually transient and may require only minimal treatment or therapeutic intervention. The event does not generally interfere with usual activities of daily living. Grade 2: A type of adverse event that is usually alleviated with additional therapeutic intervention. The event interferes with usual activities of daily living, causing discomfort but poses no significant or permanent risk of harm to the research participant. Grade 3: A type of adverse event that interrupts usual activities of daily living, or significantly affects clinical status, or may require intensive therapeutic intervention.	Grade 1: A type of adverse event that is usually transient and may require only minimal treatment or therapeutic intervention. The event does not generally interfere with usual activities of daily living. Grade 2: A type of adverse event that is usually alleviated with additional therapeutic intervention. The event interferes with usual activities of daily living, causing discomfort but poses no significant or permanent risk of harm to the research participant. Grade 3: A type of adverse event that interrupts usual activities of daily living, or significantly affects clinical status, or may require intensive therapeutic intervention.

* For all reactions but fever, subjects will record the intensity level (Grade 1, 2, or 3) in the diary card. For fever, they will record the body temperature, and the classification as Grade 1, 2, or 3 will be assigned at the time of the statistical analysis based on the unit used to measure the temperature and the intensity scale.

Important notes for the accurate assessment of temperature:

Subjects are to measure body temperature once per day, preferably always at the same time. The optimal time for measurement is the evening, when body temperature is the highest. Temperature is also to be measured at the time of any apparent fever. The observed daily temperature and the route of measurement are to be recorded in the DC/MA, and the highest temperature will be recorded by the site in the CRB. The preferred route for this study is oral. Pre-vaccination temperature is also systematically collected by the Investigator on the source document. Tympanic thermometers must not be used.

9.2.1.3.3 Unsolicited Adverse Events

In addition to recording solicited reactions, subjects will be instructed to record any other medical events that may occur between each vaccination and during the 28-day period after the last vaccination. Space will be provided in the DC for this purpose.

Information on SAEs will be collected and assessed throughout the study, from inclusion until 6 months after the last vaccination. Any SAE occurring at any time during the study will be reported by the Investigator in the CRB according to the completion instructions provided by the Sponsor; this includes checking the “Serious” box on the AE CRF and completing the appropriate Safety Complementary Information CRFs.

All information concerning the SAE is to be reported (including, but not limited to, start and stop dates, diagnosis, seriousness), either as part of the initial reporting or during follow-up reporting if relevant information became available later (eg, outcome, medical history, results of investigations, copy of hospitalization reports)

For each unsolicited AE (whether serious or non-serious), the following information is to be recorded:

- Start and stop dates^a
- Intensity of the event:

For measurable unsolicited AEs that are part of the list of solicited reactions, the size of the AE as well as the temperature for fever will be collected and analyzed based on the corresponding scale used for solicited reactions (see [Table 9.1](#) and [Table 9.2](#)).

All other unsolicited AEs will be classified according to the following intensity scale:

- Grade 1: A type of AE that is usually transient and may require only minimal treatment or therapeutic intervention. The event does not generally interfere with usual activities of daily living.

^a The stop date of all related AEs will be actively solicited. For other events, the investigator will provide the stop date when it becomes available. AEs for which no stop date was obtained during the course of the study will be considered as ongoing at the end of the study.

- Grade 2: A type of AE that is usually alleviated with additional therapeutic intervention. The event interferes with usual activities of daily living, causing discomfort but poses no significant or permanent risk of harm to the research participant.
- Grade 3: A type of AE that interrupts usual activities of daily living, or significantly affects clinical status, or may require intensive therapeutic intervention.
- Whether the AE was related to the investigational product (for unsolicited systemic AEs)
The Investigator will assess the causal relationship between the AE and the investigational product as either “Not related” or “Related”, as described in [Section 9.2.1.3.5](#).
- Action taken for each AE (eg, medication)
The action(s) taken by the subject to treat and/or manage any unsolicited AEs will be classified in the CRB using the following list (all applicable items should be checked):
 - None
 - Medication
 - Health care provider contact
 - Hospitalized
 - Discontinuation of study vaccination
- Whether the AE was serious
For each SAE, the Investigator will complete all seriousness criteria that apply (outcome, elapsed time, and relationship to study procedures)
- Whether the AE caused study discontinuation

9.2.1.3.4 Adverse Events of Special Interest (AESI)

The following AESIs will be assessed during the overall conduct of the trial:

- anaphylactic reactions
- encephalitis
- convulsions

These AESIs are considered by the Sponsor to be relevant for the monitoring of the safety profile of investigational products. They will be collected during the entire participation of a subject in the trial and are to be reported as SAEs according to the procedure described in [Section 10](#).

These AESIs have been defined based on existing post-marketing safety data (important identified or potential risks) of other rabies vaccines. For each AESI, the standard case definitions from the Brighton Collaboration will be used [\(28\)](#) [\(29\)](#) [\(30\)](#).

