	
Collection of safety data
 
Solicited injection site reactions will be recorded in the diary card (DC) in the 7 days after each injection, and unsolicited injection site reactions will be recorded during the 28 days after each injection. Subjects will record information about solicited systemic reactions in a DC between the first and the second injections, between the second and the third injections, and during the 7 days following the remaining injections. Information about unsolicited systemic adverse events (AEs) will be recorded between each injection, and during the 28 days following the last injection.
 
Subjects will record safety information in a memory aid (MA) from D56 (28 days following the last injection) until the end of the trial (month [M] 7).
 
Information about serious adverse events (SAEs), adverse events of special interest (AESIs) and cases of pregnancy will be recorded throughout the trial.
 
Study personnel will contact subjects by telephone at 6 months (+14 days) after the last vaccine injection for the collection of SAEs/AESIs.

Interruption of the Study	
The study may be discontinued if new data about the investigational product resulting from this study or any other studies become available; or for administrative reasons; or on advice of the Sponsor, the Investigators, the Independent Ethics Committees (IECs)/Institutional Review Boards (IRBs), or the governing regulatory authorities in the country where the study is taking place.
 
If the study is prematurely terminated or suspended, the Sponsor shall promptly inform the Investigators, the IECs/IRBs, the regulatory authorities, and any contract research organization(s) used in the study of the reason for termination or suspension, as specified by the applicable regulatory requirements. The Investigator shall promptly inform the study subjects and should assure appropriate subject therapy and/or follow-up.

Primary Objective:	
Immunogenicity
 
To demonstrate that VRVg-2 is non-inferior to Verorab and Imovax Rabies vaccines when co-administered with HRIG, in terms of proportion of subjects achieving a rabies virus neutralizing antibody (RVNA) titer ≥ 0.5 international units/milliliter (IU/mL) at D28, ie, 14 days after the fourth vaccine injection.

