- Oral hypoesthesia (symptoms of anxiety-related reactions or hypersensitivity), cold sweat, hyperhidrosis (symptoms of anxiety-related reactions or pyrexia), cough (symptoms of hypersensitivity) (low biological plausibility)

The VRVg-2 dose that will be used in this study has been administered to a limited number of subjects (N=80) in VRV11, following a post-exposure regimen (5 injections within 28 days) with

HRIG administration on the first day of vaccination. The AEs and frequencies reported, matched those of VRVg-1 reported as “Very common”: injection site pain, feeling unwell, headache, and muscle pain, and “Common”: fever, injection site redness and/or swelling, with the addition of injection site paresthesia, injection site hematoma/bruising, injection site pruritus, and diarrhea, also as common events. However, due to the limited sample size (N=80), events were considered as “common” even after a single occurrence of the reaction.

[REDACTED] Thus, all suspected ARs observed with Verorab (see below) are considered as possible risks for VRVg (including VRVg-1 and VRVg-2).

Thus, all identified and potential risks of Verorab are considered as potential risks for VRVg, even though they have not been observed with VRVg specifically to date.

Verorab vaccine

The following risks have been identified with the use of Verorab vaccine as currently reported in the Company Core Data Sheet:

The following AEs are derived from several clinical studies where Verorab vaccine has been used in both pre-exposure and post-exposure schedule:

- Very common (> 10%): lymphadenopathy, myalgia, injection site pain, fever, and malaise
- Common (> 1% and < 10%): skin allergic reactions, rash, pruritus (itching), edema, headache, dizziness, somnolence, abdominal pain, nausea, arthralgia, chills (shivering), injection site erythema, injection site pruritus, injection site hematoma, injection site induration, asthenia, influenza-like symptoms
- Uncommon (> 0.1% and < 1%): urticaria, angioedema, dyspnea, diarrhea, injection site edema

In addition, the following AEs have been reported during the post-marketing surveillance of the Verorab vaccine. Because these events are reported voluntarily from a population of uncertain size, it is not always possible to reliably estimate the frequency or establish a causal relationship of exposure to Verorab:

- Immune system disorders
 - Anaphylactic reactions
 - Serum sickness type reactions
- Nervous system disorders
 - Encephalitis

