 - Convulsions
- Ear and labyrinth disorders
 - Sudden sensorineural hearing loss
- Gastrointestinal disorders
 - Vomiting

Serious hypersensitivity reactions may occur after any vaccination, and they are considered important identified risks with Verorab. Other serious events listed above (encephalitis, convulsion, sudden sensorineural hearing loss) are considered important potential risks, because

although cases have been reported from post-marketing experience with Verorab, their causal association with the vaccine have not been established.

Imovax Rabies vaccine

The following risks have been identified with the use of Imovax Rabies as currently reported in the Company Core Data Sheet:

- Very common (> 10%): adenopathy, headache, nausea, myalgia, malaise, injection site pain, injection site erythema, injection site induration (swelling/hardness), and injection site hematoma
- Common (> 1% and < 10%): allergic reactions with skin disorders such as urticaria and rash, or respiratory manifestations such as dyspnea and wheezing, dizziness, abdominal pain, vomiting, diarrhea, arthralgia, injection site pruritus (itching), fever, chills (shivering)

In addition, the following AEs have been reported very rarely (< 0.01%) during the post-marketing surveillance of Imovax Rabies. Based on spontaneous reporting, their frequencies have been estimated using the number of reports and the estimated number of patients. However, the exact incidences cannot be precisely calculated.

- Immune system disorders
 - Skin allergic reactions pruritus (itching), edema
 - Anaphylactic reactions
 - Serum sickness type reactions

These reactions have been associated with the presence of betapropiolactone-altered human albumin in Imovax Rabies.

Allergic reactions occurred less frequently among persons receiving primary vaccination.

- Nervous system disorders
 - Paresthesia
 - Neuropathy
 - Convulsion, encephalitis
- General disorders and administration site conditions
 - Asthenia

HRIGs

The following AEs have been identified with the use of HRIGs (Imogam Rabies – HT) during post-marketing use, as currently reported in the Company Core Data Sheet. Because these reactions are reported voluntarily from a population of uncertain size, it is not always possible to reliably estimate their frequency or establish a causal relationship to Imogam Rabies – HT exposure. These are:

- Cardiac disorders
 - Hypotension
 - Tachycardia
- Gastrointestinal disorders

Nausea
Vomiting

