AEs of special interest are AEs that are considered by the Sponsor to be relevant for the monitoring of the safety profile of the investigational vaccine. The following AESIs are defined: anaphylactic reactions, encephalitis and convulsions.

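### Sudden sensorineural hearing loss is the only named important potential risk of Verorab left off the AESI list, with no reason given, so its expedited reporting and late capture depend on the investigator's seriousness judgement

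*Protocol*

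**What the plan says.** **Risks.** For Verorab, Protocol 1.3.2 treats serious hypersensitivity as an important identified risk and adds: "Other serious events listed above (encephalitis, convulsion, sudden sensorineural hearing loss) are considered important potential risks". The same section carries these over to the investigational vaccine: "all identified and potential risks of Verorab are considered as potential risks for VRVg".

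**AESIs.** Protocol 9.2.1.3.4 states the basis for the list: "These AESIs have been defined based on existing post-marketing safety data (important identified or potential risks) of other rabies vaccines". Protocol 9.2.1.1 gives the general definition ("AEs of special interest are AEs that are considered by the Sponsor to be relevant for the monitoring of the safety profile") and then the list: "The following AESIs are defined: anaphylactic reactions, encephalitis and convulsions". The same three events appear in the synopsis, in Protocol 9.2.1.2 and 12.1.2.2, and in SAP 3.3.1.

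**What AESI status brings.** Under Protocol 9.2.1.3.4 an AESI has an assigned case definition, is collected throughout participation and is reported as an SAE. Under Protocol 10.1 that means within 24 hours.

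**Collection over time.** Protocol 9.2.1.3.3 has subjects record "any other medical events that may occur between each vaccination and during the 28-day period after the last vaccination". After that the scope narrows. The synopsis says: "Study personnel will contact subjects by telephone at 6 months (+14 days) after the last vaccine injection for the collection of SAEs/AESIs". The memory aid handed out at V07 (Protocol 5.1.4) and the telephone questionnaire (Protocol 11.1) have the same SAE/AESI scope. SAP 3.3.1 exempts only SAEs and AESIs from the 28-day analysis period; other late events go to a separate listing.

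**The concern.** The AESI list matches the important risks named for Verorab in Protocol 1.3.2 with one item missing. Two natural explanations do not account for the gap.

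- **Unproven causality.** Protocol 1.3.2 says causality is not established for any of the three potential risks, yet two of them became AESIs.
- **SAE reporting is enough.** Protocol 1.3.2 calls all three events serious. Protocol 9.2.1.1 even uses convulsions without inpatient admission as an example of an important medical event. Convulsions are AESIs all the same, so the sponsor did not regard the ordinary SAE route as sufficient for them.

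What is at stake is the completeness and speed of safety reporting for one rare event, not the primary objective. Without AESI status, hearing loss has no assigned case definition and no automatic reporting as an SAE. Its place in the record after D56 depends on one investigator's reading of the seriousness criteria.

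**Working it through.** No sample size, power or alpha figure is involved. The check sets the sections side by side and adds simple day counts.

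**Step 1. Risk status against AESI status.**

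| Event | Status for Verorab (Protocol 1.3.2) | In the Imovax Rabies post-marketing list (Protocol 1.3.2) | AESI |
|---|---|---|---|
| Serious hypersensitivity / anaphylactic reactions | Important identified | Yes | Yes |
| Encephalitis | Important potential | Yes | Yes |
| Convulsion | Important potential | Yes | Yes |
| Sudden sensorineural hearing loss | Important potential | No | No |

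Hearing loss is the only important potential risk of the three that is not an AESI. Neither document gives a reason.

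**Step 2. The period limited to SAEs and AESIs.** Inputs: fifth injection at D28; unsolicited events recorded for 28 days after it; call 180 to 194 days after it (Protocol 5.1.4).

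- End of full unsolicited collection: 28 + 28 = D56.
- Call: 28 + 180 = D208, to 28 + 194 = D222.
- Length from D57: 208 − 57 + 1 = 152 days, to 222 − 57 + 1 = 166 days.
- Share of nominal follow-up: 152 / 208 = 73%, to 166 / 222 = 75%.

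**Step 3. What happens to a case of hearing loss.**

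| Onset | Judged serious | Judged non-serious |
|---|---|---|
| Up to D56 | Recorded; reported as an SAE within 24 hours | Recorded as an unsolicited AE and summarised by system organ class and preferred term (SAP 4.1.2.2); no 24-hour report |
| D57 to the call | Collected and analysed as an SAE | Outside the SAE/AESI scope of memory aid and questionnaire; if reported anyway, listed separately rather than summarised (SAP 3.3.1, 4.1.2.2) |

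AESI status would change the right-hand column: both cells would become reportable within 24 hours and analysable through month 7.

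**Step 4. Which cases can be judged non-serious.** A case leading to hospitalisation is an SAE under Protocol 9.2.1.1. A case managed without hospitalisation is also an SAE if it causes persistent or significant disability or is an important medical event. The gap is therefore limited to cases to which the investigator applies none of these criteria.

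**Step 5. The 6-month call.** Protocol 5.1.4 words the review at the call to include adverse events in general, medications and therapy. The synopsis and Protocol 11.1 limit it to SAEs and AESIs. On the wider wording, a late non-serious case might be elicited; on the narrower wording it is out of scope.

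**The case against.** The best case for leaving the list as it is has four parts.

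1. **No rule is broken.** Saying that the listed AESIs were based on important risks does not say that every important risk must become one, and Protocol 9.2.1.1 leaves relevance to the sponsor. This stands. A reader might infer that the protocol violates its own criterion; the text supports only an unexplained omission.

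2. **The list fits another principle.** All three AESIs appear in the post-marketing lists of both comparators, and hearing loss appears for Verorab only. That is true, but neither document states it as the selection rule. Being common to both vaccines would not produce the list on its own either: serum-sickness-type reactions appear for both and are not AESIs. If importance plus commonality was the rule, the protocol should say so.

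3. **Serious cases are collected anyway.** A reader might infer that cases managed without hospitalisation would go uncollected after D56. The documents do not support that. The disability and important-medical-event criteria do not require admission, SAEs are collected to 6 months, and Protocol 1.3.2 itself calls this event serious. What remains is that Protocol 1.3.2 describes risk and is not a reporting instruction, so each case still turns on individual judgement.

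4. **The forms are not available.** A reader might also infer that the memory aid prompts for each AESI by name and skips hearing loss. Nothing shows that any AESI is prelisted there. The SAP describes the CRF item only as a yes/no AESI question (SAP 3.3.1.2.7). The case for adding the term therefore rests on reporting rules and analysis windows, not on a missing prompt.

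**Conclusion.** The point holds, as a minor one. Of the three important potential risks named for Verorab and carried over to VRVg, only sudden sensorineural hearing loss is not an AESI, and no reason is given. The practical effect is that 24-hour reporting at any time, and planned collection and summary for 152 to 166 days after D56, depend on the investigator judging the case serious.

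The effect is bounded. Up to D56 every case is recorded whatever its seriousness. After D56 only cases judged non-serious fall outside the stated scope, and possibly not all of those if the wider wording of the 6-month call is followed. The documents give no incidence for this event, so the number of cases affected cannot be calculated; it is assumed to be very small. The day counts assume nominal visit dates, with the fifth injection at D28.

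**What to change.** - Add sudden sensorineural hearing loss to the AESI lists in the synopsis, Protocol 9.2.1.1, 9.2.1.2, 9.2.1.3.4 and 12.1.2.2, and SAP 3.3.1.
- State the case definition to be used. The existing AESIs rely on Brighton Collaboration definitions, and the protocol cites references for those three only.
- Carry the term into the AESI instructions for the CRF and the 6-month follow-up. SAP 3.3.1.2.7 derives AESI status from the CRF tick, so a change to the SAP list alone would not alter the analysis.
- If the sponsor prefers to keep the list as it is, give the reason in Protocol 9.2.1.3.4.
- Reconcile the scope of the 6-month call between Protocol 5.1.4 (adverse events generally) and the synopsis and Protocol 11.1 (SAEs and AESIs).

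The SAP version history records an amendment after unblinding of the active phase. If collection has already ended, the minimum is a targeted listing of hearing-loss terms across all reported adverse events, with the rationale for the AESI list.

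The cost is one more AESI term and case definition, and at most a few more expedited reports.
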